5.7.1.7 Blood biochemistry

The following parameters will be evaluated: sodium, potassium, calcium, phosphate, chloride, total bilirubin, alkaline phosphatase, lactate dehydrogenase (LDH), serum glutamic oxaloacetic transaminase (SGOT), serum glutamic pyruvic transaminase (SGPT), gamma-glutamyl transferase (GGT), albumin, total proteins, creatinine, urea-nitrogen, uric acid, serum iron and transferrin, albumin.

Blood chemistry will be assessed according to the schedule in [Appendix 1: Schedule of Assessments – Main Study](#) to [Appendix 5](#).

5.7.2 Vital signs and Physical Examination

Body temperature, sitting blood pressure, respiratory rate and pulse rate (after at least 5 min rest) will be assessed according to the schedule in [Appendix 1: Schedule of Assessments – Main Study](#) to [Appendix 5](#), as per standard practice at each investigational site.

Physical examination, that includes assessment of head (external), eyes, ears, nose and throat, lungs, cardiovascular system, abdomen, musculoskeletal system, skin, lymph nodes, central nervous system and, where appropriate, other body systems will be performed.

Physical examinations will be performed according to the schedule in [Appendix 1: Schedule of Assessments – Main Study](#) to [Appendix 5](#).

5.7.3 Local Injection Site Reactions

Assessment of local tolerability will be performed by examining the injection sites (by the Investigator if a reaction is present at the time of a visit) and on the basis of anamnestic data and records in the patient diary.

The abnormal injection site reaction is defined as:

- Injection site reaction which is observed at the time of visit and moderate to severe in intensity.
- Injection site reaction between the last and present visit, or remaining at the time of visit which require medical attention, or injection site reaction resulting from a previous injection, other than the last injection.
- Any other injection site reaction deemed abnormal to the investigator's judgment, other than those ordinarily observed in subcutaneous injections.

Observations will be recorded on appropriate eCRF pages. If an injection site reaction meets the criteria defined for an “abnormal result” it will be considered an AE.

- Pain and Tenderness: For patients in all Cohorts, injection site pain will be evaluated by the investigator or designated personnel if the injection is given at the medical center, and by the parent/legal guardian if the injection is given at home. The pain will be evaluated using the XXXXXXXXXX Pain Rating Scale ([Appendix 8](#)). In addition,

OPKO Biologics	Protocol for Clinical Study CP-4-004	Page 71 of 133
Effective Date: Date of final electronic approval		

each patient and parent/guardian will be queried during study visits regarding possible injection site pain.

- Site status: For patients in all Cohorts, injection site status will be evaluated by the Investigator, or designated using the Injection Site Assessment Visual Analogue Scale ([Appendix 8](#)) at each of the PK/PD sampling time points. In addition, each patient and parent/guardian will be queried during study visits regarding possible site reactions.

The Investigator's Local Assessment of Tolerability eCRF page will be designed to capture the following information.

- Description of the reaction;
- Location: left arm/right arm/left thigh/right thigh/left buttock/right buttock/left part of abdomen/right part of abdomen;
- Duration: Onset, end date;
- Intensity: grading according to the scales provided in appendices;
- Action taken: action(s) taken by patients, medical intervention or concomitant medication;
- Comments.

Patient-reported local site reactions and diary records will be captured on the "Local Tolerability assessment" CRF page. Only data about reaction type (e.g. pain, erythema, etc.), frequency, and intensity will be captured.

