2.1 STUDY OBJECTIVES

2.1.1 Primary Objectives

The primary objectives are to compare the safety, efficacy and tolerability of three MOD-4023 doses to that of a commercially available standard daily r-hGH formulation, in pre-pubertal children with growth failure due to insufficient secretion of endogenous growth hormone.

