Patients allocated to Cohort 4 will perform Visits 2 and 4. Cohort 4 patients will skip Visit 3 (week 4).

Patients allocated to the Genotropin cohort (cohort 4) will return to the medical center for visits 2 and 4 during the 2nd and 6th week of treatment. The following procedures will be performed (prior to dosing if dosing is done at the medical center):

1. Physical examination;
2. Vital signs;
3. AEs, local tolerability;
4. Concomitant medications;
5. Parameters of glucose metabolism - fasting glucose, insulin, and HbA1C (V4 only);
6. Routine safety biochemistry, hematology, and urinalysis parameters (week 6 only – visit 4);
7. IGF-I and IGFBP-3 serum levels;
8. Genotropin serum levels.

In addition, after the 8th Genotropin dose (at the beginning of week 2 of dosing) the patients allocated to the Genotropin cohort will undergo limited PK/PD sampling according to [Table 7](#) above. Patients allocated to the Genotropin dose cohort (cohort 4) will be randomized within the cohort into one of three blocks and undergo limited PK/PD sampling (4 samples per patient over a period of 24 hours), according to following scheme:

OPKO Biologics	Protocol for Clinical Study CP-4-004	Page 55 of 133
Effective Date: Date of final electronic approval		

Time after dosing(h)/ Block number	0h	1h	2h	4h	6h	12h	16h	20h	24h
Block 1									
Block 2									
Block 3									

5.1.4 Monthly Follow Up Visits: Visit 5 (wk10), Visit 6 (wk14), Visit 7 (wk18), Visit 8 (wk22) - All Patients

These visits will be performed on a monthly basis for all patients. For patients allocated to MOD-4023 dose cohorts, the visit will take place 4(-1) days after dosing. For patients allocated to Genotropin cohort, the visit will take place on any day during the dosing week.

The following assessments will be performed:

1. Physical examination and vital signs;
2. AEs, local tolerability, and concomitant medications;
3. Parameters of glucose metabolism: fasting glucose, insulin (every visit), HbA1c (only visit 6);
4. Other hormonal levels: TSH, free T4, free T3, cortisol (only visit 6);
5. Routine safety biochemistry, hematology, and urinalysis parameters;
6. Patient's height;
7. Patient's weight;
8. Parameters of lipid metabolism (with Lp(a) lipoprotein at visit 6);
9. PD: IGF-I and IGFBP-3 serum levels;
10. MOD-4023 (cohort 1-3) and Genotropin (cohort 4) serum levels;
11. Adjustment of dose to patient's weight (only visit 6).

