Return and accountability of study medication														X	X	X	
Return and review of patient diary														X	X	X	

¹ Dose adjustment will be made according to weight measured on three monthly bases.

² Heart rate, blood pressure, body temperature, respiratory rate.

³ Only for patients for which the insulin-stimulation test has not been used or glucagon test has shown peak cortisol level below 500 nmol/l. Will be done at any point during the study if there is suspicion of de novo hypoadrenalinism.

OPKO Biologics	Protocol for Clinical Study CP-4-004	Page 111 of 133
Effective Date: Date of final electronic approval		

⁴ Earlier if there are clinical signs of intracranial hypertension.

⁵ Vital signs: for all patients allocated to cohorts 1- 3 (MOD) - Pre-dose and at 30 mins, 2h (\pm 20 mins) and 4h (\pm 20mins); for patients in cohorts 4 (Genotropin) at any time during the visit.

⁶ Injection site reaction: 30 min and 4h (\pm 20 min) post dosing for MOD-4023 cohorts and at any time during the visit for patients in cohort 4 (Genotropin).

⁷ Insulin tolerance test, with cortisol response to hypoglycemia if insulin stimulation test is chosen / Arginine test / Clonidine test / Glucagon test (plus or without propranolol) / L-dopa plus propranolol. At least one of the two stimulation tests must be analyzed by the central lab.

⁸ with Lp(a) lipoprotein.

⁹ Last MOD-4023 dosing 4 (-1) days before V12.

¹⁰ Last Genotropin dosing 1 day before V12.

OPKO Biologics	Protocol for Clinical Study CP-4-004	Page 112 of 133
Effective Date: Date of final electronic approval		

MOD-4023 Dose Cohorts (Cohorts 1-3) PK/PD Sampling Scheme

Visit	a		b	c	d	e	f	g	
Time after dosing(h)/ Block number	0h	6h	12h	24h	48h	72h	96h	120h	168h
Block 1	3.5 ml			3.5 ml	3.5 ml		3.5 ml		
Block 2		3.5 ml			3.5 ml	3.5 ml		3.5 ml	
Block 3			3.5 ml	3.5 ml		3.5 ml			3.5 ml

Genotropin Dose Cohort (Cohort 4) PK/PD Sampling Scheme

Time after dosing(h)/ Block number	0h	1h	2h	4h	6h	12h	16h	20h	24h
Block 1	3.5 ml		3.5 ml	3.5 ml			3.5 ml		
Block 2		3.5 ml		3.5 ml	3.5 ml			3.5 ml	
Block 3			3.5 ml		3.5 ml	3.5 ml			3.5 ml

OPKO Biologics	Protocol for Clinical Study CP-4-004	Page 113 of 133
Effective Date: Date of final electronic approval		

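### One injection-site AE criterion depends on the dosing interval: on its most natural reading, a mild reaction of about 2 to 6 days can meet it on daily Genotropin but not on weekly MOD-4023

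*Protocol*

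**What the plan says.** Protocol section 5.7.3 lists three bullets that define an abnormal injection-site reaction. If a reaction meets them, "it will be considered an AE".

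- The first bullet needs a reaction "observed at the time of visit and moderate to severe in intensity".
- The second covers reactions since the last visit, or still present, that need medical attention. It then adds an "injection site reaction resulting from a previous injection, other than the last injection", with no grade, duration or elapsed time.
- The third is a judgment route: "Any other injection site reaction deemed abnormal to the investigator's judgment".

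None of these has an arm-specific version. MOD-4023 is injected weekly and Genotropin every day at bedtime (synopsis; section 6.1.4). At the monthly visits in section 5.1.4, for MOD-4023 cohorts "the visit will take place 4(-1) days after dosing"; Genotropin children attend on any day of the dosing week.

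Section 2.1.1 states: "The primary objectives are to compare the safety, efficacy and tolerability of three MOD-4023 doses" with daily r-hGH. Section 8.5 rests the safety assessment mainly on AE frequency. The SAP supplied covers only the extension periods, in which every child receives MOD-4023, so it neither uses nor corrects the Main Study comparison.

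**The concern.** The criterion appears intended to pick out reactions that persist. It measures persistence by whether another injection has been given since, and that depends on the regimen rather than on the skin. Two children with the same mild reaction lasting the same number of days can be classified differently because one is injected daily and the other weekly.

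Tolerability against daily r-hGH is part of the primary objective, and AE frequency by cohort is the main safety summary. A persistence threshold that is shorter in the comparator arm adds comparator AEs by definition. Section 1.4.1 already draws on the Main Study's 12-month safety and tolerability outcome, so the basis of that comparison should be clear.

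**Working it through.** The plan states no figure on this point, so there is none to reproduce. The check applies the rule to the two regimens.

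**Inputs.** Dosing interval: 1 day for Genotropin, 7 days for MOD-4023 (synopsis; section 6.1.4). MOD-4023 routine visits: 3 to 4 days after a dose (section 5.1.4). Assumption: a Genotropin child is seen in the daytime, about 0.5 day after the bedtime dose (section 5.6 prefers morning height measurement). Reaction rates and durations: not given.

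**Step 1, threshold on the most natural reading.** A reaction of duration D meets the criterion once D exceeds the dosing interval: more than 1 day on Genotropin, more than 7 days on MOD-4023. At a visit, the age of the injection before the last is the time since the last dose plus one interval:

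- Genotropin: 0.5 + 1 = 1.5 days.
- MOD-4023, day 4(-1) visit: 3 + 7 = 10 to 4 + 7 = 11 days.
- MOD-4023, just after a dose on a dosing day: 0 + 7 = 7 days.

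This assumes doses on schedule. Section 6.1.2 allows a dose up to 72 h late followed by a return to the usual day, which can shorten one weekly interval to 7 − 3 = 4 days.

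**Step 2, earlier injections that could still show a reaction at a routine visit.**

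| Duration D | Genotropin (ages 1.5, 2.5, 3.5, ... below D) | MOD-4023, day 3-4 visit |
|---|---|---|
| 2 days | 1 | 0 |
| 4 days | 3 | 0 |
| 6 days | 5 | 0 |

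**Step 3, why no size can be stated.** Suppose each injection gives a mild reaction of duration D with probability p, independently. The chance of at least one qualifying reaction at a Genotropin visit is 1 − (1 − p)^k, with k from the table:

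- p = 2%, D = 2: 1 − 0.98^1 = 2.0%
- p = 5%, D = 4: 1 − 0.95^3 = 14.3%
- p = 10%, D = 6: 1 − 0.90^5 = 41.0%

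The matching MOD-4023 value is 0% each time. Both p and D are assumed, and the answer runs from 2% to 41% with them. Part of it also reflects that daily dosing gives seven times as many injections, which is a real treatment difference and not a matter of definition.

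**Step 4, the other readings of the second bullet.**

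- Any reaction since the last visit, from any injection but the last. Over 4 weeks, MOD-4023 has 4 injections, of which 3/4 = 75.0% are eligible; Genotropin has 28, of which 27/28 = 96.4% are eligible. Over 13 weeks the shares are 12/13 = 92.3% and 90/91 = 98.9%. The gap is smaller and in the same direction.
- The medical-attention condition governs the whole bullet. Mild reactions that need no attention drop out in both arms, and the gap disappears.

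The first reading is preferred because the final clause repeats its own subject after the conjunction and so stands as a separate criterion. The since-last-visit reading would leave the medical-attention condition with almost nothing to do for reactions between visits.

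**The case against.** The strongest reply is that the bullet is badly worded and the gap depends on how a site reads it. Reactions are collected from history and diary as well as by examination, which gives the since-last-visit reading some support. This stands: the gap may be large, small or absent. But a rule that sites could apply in three ways is itself a reason to fix it, and no reading reverses the direction for this criterion.

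It can also be said that section 2.2 lists local injection-site assessment as its own endpoint and that section 8.5 summarises graded local tolerability independently of AE status. That is so, but section 8.5 ties that summary to the intensive PK/PD sampling, and it does not repair AE incidence over 12 months. The analyses are exploratory, with no hypothesis tests (section 8.1). That limits the consequence but does not make a biased descriptive comparison sound.

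The point about the remedy also stands in part. Genotropin was used only in the Main Study, so rewording cannot change what was collected, and the diary-based page holds type, frequency and intensity but no dates (section 5.7.3).

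A reader might go further and infer a bias of known size from the first bullet. MOD-4023 has 3 dosing-day visits (V1, one PK visit, V9), and Genotropin has 9 visits within about a day of an injection. At an assumed 5% per visit that gives 1 − 0.95^3 = 14% against 1 − 0.95^9 = 37%, a ratio of 2.6. The documents do not support this. The first bullet has no 24 h limit, so a moderate reaction still visible at a day 3-4 MOD-4023 visit counts too. Counting every visit once, with the PK week as one, gives 11 (cohort 1) or 12 (cohorts 2 and 3) for MOD-4023 against 9. At the same 5% that is 43% to 46% against 37%, which reverses the order. MOD-4023 children also have set inspections at 30 min and 4 h after dosing, while Genotropin children have no set time (Appendix 1, footnote 6). No ratio or direction can be claimed for that bullet.

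**Conclusion.** The second bullet of section 5.7.3 sets a persistence threshold that varies with the regimen. On its most natural reading the threshold is about 1 day on Genotropin and 7 days on MOD-4023 (10 to 11 days at a day 4(-1) visit), so mild reactions of about 2 to 6 days can meet it in the comparator arm only. This rests on doses given on schedule and a daytime Genotropin visit.

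It does not follow that every such reaction is an AE on Genotropin and never on MOD-4023. Medical attention or investigator judgment can make it an AE in either arm, and the other two readings shrink or remove the gap. Where a gap exists, this criterion favours MOD-4023. Its size cannot be found from the documents, and the net effect of all three bullets on the tolerability comparison is not established. The point still merits action, because it affects AE frequency in a comparison named in the primary objective and is cheap to correct.

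**What to change.** In section 5.7.3, replace the reference to an injection before the last with one fixed elapsed time since the causing injection, identical in all cohorts, and state whether the medical-attention condition applies to that clause. The value is for the sponsor to set.

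For the Main Study comparison:

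- apply that rule to reactions whose onset and end dates are on the Investigator's Local Assessment of Tolerability page, using the recorded location and the dosing record to identify the injection where possible;
- summarise graded reactions by cohort regardless of AE status, from the investigator assessments and from diary type, frequency and intensity;
- state in the report that injection-site AE incidence under the present rule is not comparable between the weekly and daily arms.

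The cost is a wording change and a modest re-analysis of data already collected. Reactions recorded only in the diary cannot be re-derived because they carry no dates, so for them the graded summary is all that is available. Some injection-site AEs may be reclassified; how that would move the comparison cannot be predicted from the documents.

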5.7.4 Fundoscopy and MRI

Fundoscopy (ophthalmoscopy) will be performed by the Investigator or an ophthalmologist consultant in order to assess signs of increased intracranial pressure prior to initiating or as a result of GH replacement. At screening (or within 6 months prior to screening), to confirm the diagnosis of GH deficiency and to confirm that there is no evidence of pituitary adenoma or any other intracranial tumor, a magnetic resonance imaging scan (MRI) with contrast will be done. It will be performed by the relevant department of the hospital according to the routine practice. During the study, MRIs may be performed per the investigator's discretion, (i.e. when there is suspicion of either growth of pituitary adenoma or any other intracranial tumor).

Fundoscopy will be performed according to the schedule in [Appendix 1: Schedule of Assessments – Main Study to Appendix 5](#).

5.7.5 ECG

ECG will be performed according to the schedule in [Appendix 1: Schedule of Assessments – Main Study to Appendix 5](#).

In the first year of the LT-OLE-PEN period ECG will be performed once a year on 12 months visit around Tmax (7 to 12 hours post injection). In case not possible to conduct the ECG around Tmax at this 12 month visit, it can be performed on month 12 ± 3 weeks (7-12 hours post dose). Adverse Events

OPKO Biologics	Protocol for Clinical Study CP-4-004	Page 72 of 133
Effective Date: Date of final electronic approval		

Adverse events (AEs) will be assessed immediately following the written informed consent and assent (if applicable) and at all study visits throughout the study. Any AEs that occur throughout the study will be recorded. Any new systemic AE that occurs between scheduled visits should be brought to the attention of the Investigator and recorded in the patient's medical file and on the appropriate eCRF page.

For a list of common AEs associated with human GH, please refer to the Investigator's brochure.

5.8 DOSE MODIFICATION AND DISCONTINUATION

The following symptoms and laboratory abnormalities measured at a single occasion or repeatedly, are considered to be the main guide for the decision about dose modification or treatment interruption:

- Growth factors plasma levels:
 - **Repeated consecutive IGF-I > +2.0 SDS**
- Glucose tolerance
 - HbA1c level > 6.2 %
 - Fasting glucose level is > 5.5 mmol/L
- Increase of liver enzymes ($\geq 2x$ of ULN)
- Immune response
 - Development of high anti-growth hormone antibody titre with strong neutralizing effect
- Any other CTC grade 3 or 4 laboratory abnormality
- Development of intracranial hypertension or pseudotumor cerebri - If a patient has persistent severe headaches for more than 1 day not relieved by aspirin or other analgesics or visual disturbances, then examine the patient for papilledema (to be confirmed by an ophthalmologist). If there is papilledema, perform an MRI of the head with contrast; if there are signs of intracranial hypertension, perform a lumbar puncture (LP) and record the opening pressure. Only positive MRI findings and increased opening pressure on LP confirm the diagnosis of pseudotumor.

In the Main Study, dose efficacy will be analysed first after 6 months of treatment on an individual patient level. Patients who do not achieve the minimally satisfactory growth rate (i.e. delta height SDS of at least 0.2) at this time point will be moved to the next highest dose group for the remaining 6 months of treatment. Dose efficacy will be analysed again after 12 months of treatment on an individual patient level. Patients who do not achieve the minimally satisfactory growth rate at this time point will be moved to the next highest dose group. If the patient is in the highest dose group, the Coordinating Investigator of the study will be informed.

OPKO Biologics	Protocol for Clinical Study CP-4-004	Page 73 of 133
Effective Date: Date of final electronic approval		

Cohort 1-3 patients transitioning to the OLE will continue with the same dose (mg/kg) in which they completed the main study.

In the OLE period, the patients who were in cohort 4, in the main study (e.g. treated with Genotropin) will be randomized to one of the MOD-4023 treatment groups.

In the LT-OLE period, all patients will be switched to the highest MOD-4023 dose 0.66 mg/kg/week.

In the LT-OLE-PEN period, patients should continue with the same dose.

The dose modifications will be performed according to the same rules as in the main study, including adjustment for weight every 3 months.

5.8.1 Dose Modifications Based on Adverse Effects (main study)

If a patient develops a **severe GH-related adverse event** at any time during the course of the study (Main and OLE), the Sponsor, the Coordinating Investigator, the investigator or the Data Safety Monitoring Board (DSMB) may propose one of three options:

1. **If the patient is allocated to Cohort 1 (0.25 mg protein/kg/week)** the following dose will not be given. If the symptoms disappear, the patient will continue on the same dose level as initially allocated. In case the symptoms reoccur, the patient may be withdrawn from the study.
2. **If the patient is allocated to Cohort 2 (0.48 mg protein/kg/week)** the dose will be lowered to the lower dose level (0.25 mg/kg/week) for a 2-4 week period. The patient may be re-challenged, once the symptoms disappear, with the same dose level as initially allocated. In case symptoms reoccur, the patient may be kept on the reduced dose level.
3. **If the patient is allocated to Cohort 3 dose (0.66 mg protein/kg/week)** the dose will be reduced by 15% to 0.56 mg/kg/week. If the symptoms are resolved, the patient will continue on the same dose level.

In case the AE is persist or the symptoms reoccur the dose will be reduced again by 15% to 0.48 mg/kg/week. Patients, who had their dose reduced twice and who still have symptoms or they reoccur will be required to have individual medical consultation, depends on AE and /or symptoms assessment.

It is recommended to consult with study Medical Monitor prior to dose changes (the Medical Monitor must be informed of such a change after the event if prior consultation is not possible).

4. **Patient will be withdrawn from the study either:**

- Without attempt of dose reduction if such a severe AE(s) develops that may affect patient safety and wellbeing.
- If symptoms do not disappear after the transient dose interruptions or dose reductions (Please see case 1-3 above).

OPKO Biologics	Protocol for Clinical Study CP-4-004	Page 74 of 133
Effective Date: Date of final electronic approval		

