5.8.3 Dose adjustment paradigm

Doses may be decreased for safety reasons according to the pre-defined dose-adjustment criteria (which will be based on the severity of AEs or repeated, elevated levels of IGF-I SDS).

The dose will be decreased based on two repeated day 4(-1) levels of IGF-I $> +2.0$ Standard Deviation Score (SDS).

[figure not shown]
If a patient has an IGF-I level above +2.0 SDS, they will be requested to return for an unscheduled visit within 4-6 weeks after the $>+2.0$ SDS result, on day 4(-1) post dose. If their IGF-I level is still above +2.0 SDS, the most recent dose will be reduced by 15% (i.e. in case the starting dose is 0.66 mg/kg/week, reduction to 0.56 mg/kg/week). The patient will be treated with the new dose for at least 4 weeks before a subsequent IGF-I determination can result in a further dose modification. If the next scheduled visit is less than 4 weeks after the dose reduction was effectuated, the IGF-I result at that visit must NOT be used for additional dose recalculation. At the time of the next visit (or at an extra, unscheduled visit which complies with the 4 week minimum time period), IGF-I will be resampled. If the IGF-I is still above +2.0 SDS, the dose will be reduced an additional 15% (i.e. in case the starting dose is 0.66 mg/kg/week, reduction to 0.48 mg/kg/week). If the IGF-I is still above +2.0 SDS following 2 dose reductions (at least 4 weeks after second dose reduction), the sponsor Medical Monitor (with the assistance of the DSMB if necessary) will decide on course of treatment on an individual basis.

If AEs are defined as “severe” and drug-related, dose reduction will be introduced upon discussion with Sponsor Medical Monitor and DSMB - dose should be reduced at a similar manner as above in two step approach.

OPKO Biologics	Protocol for Clinical Study CP-4-004	Page 75 of 133
Effective Date: Date of final electronic approval		

Figure 2: Overall Dose Adjustment Scheme

This figure is an example for a dose of 0.66 mg/kg/week. The rules also applies for patients who receive lower doses.

OPKO Biologics	Protocol for Clinical Study CP-4-004	Page 76 of 133
Effective Date: Date of final electronic approval		

6. Investigational Product

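### For a severe related adverse event, Protocol 5.8.1 and 5.8.3 give different dose handling below 0.66 mg/kg/week with no order of precedence, and 5.8.1 disagrees with itself on its scope and on withdrawal

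*Protocol*

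**What the plan says.** **Protocol 5.8.1.** The heading limits the section to the main study, but the text applies it "at any time during the course of the study (Main and OLE"). For a severe GH-related event, the sponsor, Coordinating Investigator, investigator or DSMB "may propose one of three options". Four numbered items follow:

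- Option 1 (Cohort 1, 0.25 mg/kg/week): "the following dose will not be given". If symptoms clear, the child resumes the allocated dose.
- Option 2 (Cohort 2, 0.48 mg/kg/week): "the dose will be lowered to the lower dose level (0.25 mg/kg/week) for a 2-4 week period". Re-challenge at 0.48 is possible once symptoms clear.
- Option 3 (Cohort 3, 0.66 mg/kg/week): a 15% cut to 0.56 and, if needed, a second to 0.48. Children with symptoms after both cuts "will be required to have individual medical consultation, depends on AE and /or symptoms assessment".
- Item 4: the child is withdrawn in either of two situations. One is "If symptoms do not disappear after the transient dose interruptions or dose reductions", with an explicit pointer back to cases 1 to 3.

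Consulting the Medical Monitor before a dose change is recommended. If that is not possible, the Monitor must be told afterwards.

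**Protocol 5.8.3.** The IGF-I rule takes 15% off the most recent dose, up to twice. For events that are severe and drug-related, "dose should be reduced at a similar manner as above in two step approach", after discussion with the Medical Monitor and the DSMB. The note to Figure 2 calls the 0.66 scheme an example and adds: "The rules also applies for patients who receive lower doses".

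**The concern.** Both sections address the same situation, a severe event attributed to the drug, and below 0.66 mg/kg/week they prescribe different actions. No sentence says which one governs. Period does not separate them: the text of 5.8.1 reaches into the OLE, and the end of Protocol 5.8 carries the main-study modification rules into the later periods. Dose level does not separate them either, because of the Figure 2 note.

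The main stake is consistent handling of severe events in children. There is also a reporting stake. The OLE SAP makes safety its primary objective, refers to the protocol's dose-adjustment rules (SAP 4 and 4.2), summarises dose adjustments by reason (SAP 9.13), and has separate tables for adverse events leading to drug withdrawal, to reduction or interruption, and to study discontinuation (SAP 11.1, Tables 6.1.1 to 6.1.3). Which of these tables a child enters can depend on which paragraph was applied.

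**Working it through.** **Inputs.** Doses of 0.25, 0.48 and 0.66 mg/kg/week (Protocol Table 8); 15% of the most recent dose per step (5.8.3); stated steps 0.66 to 0.56 to 0.48 (5.8.1 option 3 and 5.8.3).

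**Step 1: reproduce the plan's own figure.** With a factor of 0.85 per step, 0.66 × 0.85 = 0.561 and 0.561 × 0.85 = 0.477. These round to the stated 0.56 and 0.48. Taking 15% of the starting dose twice would give 0.66 × 0.70 = 0.462, which does not match, so the steps compound. At 0.66 the two sections agree on the reductions.

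**Step 2: the cut in 5.8.1 for Cohort 2.** (0.48 − 0.25) / 0.48 = 47.9%, for 2 to 4 weeks.

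**Step 3: 5.8.3 at the lower doses, assuming that a similar manner means 15% per step.**

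- Cohort 2: 0.48 × 0.85 = 0.408; 0.408 × 0.85 = 0.347.
- Cohort 1: 0.25 × 0.85 = 0.2125; 0.2125 × 0.85 = 0.181.

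The protocol does not state these four doses. Without compounding, the second step would be 0.336 and 0.175, so the comparison hardly depends on that choice.

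**Step 4: side by side.**

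| Situation | 5.8.1 | 5.8.3 (15% reading) |
|---|---|---|
| Cohort 1 | One dose omitted, then 0.25 again | 0.21, then 0.18 if needed |
| Cohort 2 | 0.25 for 2 to 4 weeks, then possibly 0.48 again | 0.41, then 0.35 if needed; no re-challenge stated |
| Cohort 3 | 0.56, then 0.48 if needed | 0.56, then 0.48 if needed |
| Prior oversight | Medical Monitor consultation recommended | Discussion with Medical Monitor and DSMB |

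For Cohort 2 the two rules differ in both directions. Section 5.8.1 gives the lower dose at first (0.25 against 0.41) and the higher dose after a successful re-challenge (0.48 against 0.41 or 0.35).

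**Step 5: inside 5.8.1.** Take a Cohort 3 child whose symptoms have persisted through both reductions. Option 3 requires an individual consultation and fixes no outcome. Item 4 expressly includes case 3 and states withdrawal as the outcome. Read literally, one leaves the result open and the other does not. Protocol 4.6 adds a third wording: after a severe adverse drug reaction, participation may be discontinued if the patient wishes it or if the investigator or Medical Monitor considers it necessary.

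**The case against.** The strongest reply is that the dose-step conflict has limited reach now. Main Study results were already known when this protocol version was written (Protocol 1.4.1). LT-OLE moves lower-dose children to 0.66 mg/kg/week, where the sections agree; Protocol 5.3 excepts children for whom a different medical decision was made. This stands and sets the size of the point.

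The second reply is that 5.8.3 asks only for similarity and gives no percentage in its adverse-event sentence. The surrounding text is mostly about IGF-I, and Figure 2 is not available to show whether it covers adverse events. This also stands: a reader might take 0.41, 0.35, 0.21 and 0.18 as prescribed doses, but they are one literal reading. The conflict survives without them, because a two-step reduction of any size is neither an omitted dose followed by resumption nor a temporary drop to 0.25 with re-challenge.

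Third, a reader might infer that sites may follow whichever rule they prefer. The documents do not support that. Both sections involve the Medical Monitor, and 5.8.3 adds the DSMB. Oversight limits divergence between sites, although the two sections ask for different degrees of it.

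Fourth, consultation and withdrawal need not exclude each other, since a consultation can end in withdrawal. Nor does option 3 say that the child continues on treatment, though a reader might infer it. The remaining difficulty is that item 4 makes withdrawal mandatory where option 3 leaves the decision to an assessment.

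Finally, announcing three options and listing four items is editorial: there are three cohort-specific actions plus withdrawal.

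**Conclusion.** The point holds as a contradiction between stated rules. Below 0.66 mg/kg/week, 5.8.1 and 5.8.3 direct different actions for a severe related event and neither has precedence. For Cohort 2 the contrast is a temporary 48% cut against, on the 15% reading, a first step to about 0.41 mg/kg/week. For Cohort 1 it is an omitted dose with no later reduction against a reduced dose. This mainly affects Periods I to III and any child kept on a lower dose afterwards.

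Two conflicts inside 5.8.1 stand apart from this: heading against text on scope, and option 3 against item 4 for a child on 0.66 still symptomatic after two reductions. The second matters more from now on, because LT-OLE moves children to 0.66 and the PEN period continues their dose.

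The conclusion assumes that GH-related in 5.8.1 and drug-related in 5.8.3 describe the same trigger; the protocol draws no distinction. It relies on the Figure 2 note alone for the reach to lower doses. A reader might infer that the OLE results are compromised. The documents do not show that: no frequency of severe related events is given, Protocol 1.4.1 reports no withdrawal for a MOD-4023-associated event in the 12-month data, and the SAP keeps dose-adjusted children in their main dose groups and pools all children after the first OLE year. No power or error-rate figure depends on this point. It should be corrected because it governs how severe events in children are handled.

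**What to change.** Reconcile 5.8.1, 5.8.3 and the Figure 2 note in one amendment:

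1. State which section governs severe related adverse events in each study period and at each dose level.
2. State what a similar two-step reduction means for adverse events, and whether the Figure 2 note applies to them.
3. Make the 5.8.1 heading and text agree on scope.
4. Make option 3 and item 4 agree for a child still symptomatic after two reductions, and check the result against Protocol 4.6.
5. Use one statement of the Medical Monitor and DSMB involvement needed before a dose change.

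Which clinical rule to adopt is for the sponsor; this review takes no position. The cost is protocol wording only, with no change to the sample size or analysis methods.
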